2.6.2 Expansion Phase

The doses used in the Expansion Phase will be the MTD or MAD for the combination of MGA271 and pembrolizumab determined during the Dose Escalation Phase.

3 STUDY PURPOSE AND OBJECTIVES

This study is an open-label, dose escalation, Phase 1 study designed to characterize the safety, tolerability, PK, pharmacodynamics (PD), immunogenicity, and preliminary antitumor activity of IV MGA271 administered IV weekly in combination with 2 mg/kg pembrolizumab administered IV every 3 weeks in patients with unresectable locally advanced or metastatic melanoma, NSCLC, SCCHN, urothelial cancer, and other cancers. With Amendment 5, a new cohort (Cohort 4) will be initiated to explore the safety, tolerability, PK, PD, and immunogenicity of MGA271 + MGA012, both administered Q3W, in patients with unresectable locally advanced or metastatic melanoma, NSCLC, SCCHN, urothelial cancer, and other cancers, as stipulated in [Section 5.1](#), Inclusion Criteria.

3.1 Primary Objective

The primary objectives of this study are:

- To characterize the safety, tolerability, DLT, and MTD, or MAD (if no MTD is defined) of MGA271 when administered IV weekly in combination with 2 mg/kg pembrolizumab administered IV every 3 weeks (Q3W) to patients with unresectable locally advanced or metastatic melanoma, SCCHN, NSCLC, urothelial cancer, and other cancers.
- To characterize the safety, tolerability, and DLT of 15 mg/kg MGA271 when administered IV Q3W in combination with a flat-dose of 375 mg of MGA012 (anti-PD-1 antibody) administered IV Q3W to patients with unresectable locally advanced or metastatic melanoma, SCCHN, NSCLC, urothelial cancer, and other cancers as stipulated in inclusion criteria.

3.2 Secondary Objective(s)

Secondary objectives of this study are:

- To characterize the PK and immunogenicity of MGA271 administered IV weekly in combination with IV pembrolizumab Q3W, and of MGA271 in combination with MGA012, both administered IV every 3 weeks.
- To characterize the PD activity of MGA271 when administered IV weekly in combination with pembrolizumab Q3W, and of MGA271 in combination with MGA012, both administered IV Q3W.
- To investigate the preliminary antitumor activity of MGA271 when administered IV weekly in combination with IV pembrolizumab Q3W, and of MGA271 in combination with MGA012, both administered IV Q3W using both conventional Response Evaluation Criteria in Solid Tumors (RECIST) 1.1 ([Appendix 5](#)) and immune-related response criteria (irRC) (i.e., irRECIST as defined in [Appendix 6](#)).

3.3 Exploratory Objectives

- To explore the relationships between PK, PD, patient safety and antitumor activity of MGA271 when administered in combination with pembrolizumab.
- To investigate the immune-regulatory activity of MGA271 in combination with pembrolizumab and of MGA271 in combination with MGA012 *in vivo*, including various measures of T cell activation in peripheral blood and/or tumor biopsy specimens.
- To determine the relationships between membranous expression of B7-H3 and PD-L1 on tumor cells, immune cell infiltration within biopsy specimens (including but not limited to CD4+ and CD8+ T cells), B7-H3 and PD-L1 expression on the immune cell infiltrate, and clinical response via IHC staining of optional paired pre- and on-treatment tumor biopsy specimens.

4 TRIAL DESIGN

[figure not shown]
4.1 Overall Study Design and Plan

4.1.1 General Study Design

This study is a Phase 1, open-label, dose escalation and cohort expansion study designed to characterize the safety, tolerability, PK, PD, immunogenicity, and preliminary antitumor activity of MGA271 administered IV weekly in combination with pembrolizumab administered IV every 3 weeks (Q3W). Beginning with Amendment 5, this study will also characterize the safety and tolerability of MGA271 in combination with MGA012 (anti-PD-1 antibody), both administered by IV, Q3W, through the addition of a new cohort, Cohort 4.

The study consists of a **Dose Escalation Phase** to determine the MTD or MAD (if no MTD is determined) of MGA271 administered in combination with 2 mg/kg pembrolizumab, followed by a **Cohort Expansion Phase** to further define the safety and initial efficacy of the combination with the MGA271 dose established in the first phase. The study treatment schema is presented in **Figure 2**.

Figure 2 MGA271 + Pembrolizumab Treatment Schema

a Patients may receive up to 5 subsequent 9-week treatment cycles of MGA271 + pembrolizumab depending on response to study treatments

*All patients will enter an Efficacy Follow-up Period after receipt of the last dose of study treatment to be followed for up to 24 weeks for survival.

[figure not shown]
MGA271 will be administered as an IV infusion over 120 minutes on a once-weekly schedule. Pembrolizumab will be administered at 2 mg/kg as an IV infusion over 30 minutes every 3 weeks. On the days that both agents are administered, pembrolizumab will be administered first, followed by MGA271.

For both the Dose Escalation and Cohort Expansion phases, patients' first tumor assessment will be obtained on Cycle 1 Study Day 42 of the **Initial Tumor Assessment Cycle**.

Patients who remain clinically stable and do not experience unacceptable toxicity that necessitates permanent discontinuation of the study drugs, at the completion of the Initial (6-week) Tumor Assessment Cycle will be eligible to receive additional treatment with pembrolizumab and MGA271. Assuming that the patient remains clinically stable, maintains a response status of SD or better, and does not experience unacceptable toxicity that necessitates permanent discontinuation of the study drugs, patients may receive up to 5 additional 9-week treatment cycles during **Subsequent Tumor Assessment Cycles**, for a maximum total of 51 doses of MGA271 and 17 doses of pembrolizumab.

Beginning with Amendment 5, in Cohort 4: 15 mg/kg MGA271 will be administered as an IV infusion over 120 minutes Q3W in combination with 375 mg MGA012 administered as an IV infusion over 60 to 75 minutes Q3W. On dosing days, MGA012 will be administered first, followed by MGA271. The study treatment schema is presented in **Figure 3**.

Figure 3 **MGA271 + MGA012 Treatment Schema: Cohort 4**

a Patients may receive up to 5 subsequent 9-week treatment cycles of MGA271 + MGA012 depending on response to study treatments

▲ All patients will enter an Efficacy Follow-up Period after receipt of the last dose of study treatment to be followed for up to 24 weeks for survival.

Patients who remain clinically stable and do not experience unacceptable toxicity that necessitates permanent discontinuation of the study drugs, at the completion of the Initial (6-week) Tumor Assessment Cycle, will be eligible to receive additional treatment with MGA271+MGA012. Assuming that the patient remains clinically stable, maintains a response status of SD or better, and does not experience unacceptable toxicity that necessitates permanent discontinuation of the study drugs, patients may receive up to 5 additional 9-week treatment cycles during **Subsequent Tumor Assessment Cycles**, for a maximum total of 17 doses of MGA271 and 17 doses of MGA012.

All tumor assessments performed following the Initial Tumor Assessment Cycle will occur on Study Day 63 of each Subsequent Tumor Assessment Cycle thereafter. Following the last dose of study drug, all patients will be followed for survival during a 6-month (24-week) **Efficacy Follow-up Period**. Patients who discontinue study treatment for a reason other than progressive disease may be followed for efficacy and survival beyond the 6-month (24-week) period until 1 of the following occurs: the patient progresses, withdraws consent for follow up, or initiates other anti-cancer therapy, or the overall trial is closed.

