4.1.4 Efficacy Follow-up Period

The **Efficacy Follow-up Period** consists of the 6-month (24-week) period following the final dose of study drug (pembrolizumab or MGA271 or MGA012, whichever is last) where patients will be followed for survival via telephone or other electronic contact at 12-week intervals from the start of the period. Patients who discontinue study treatment for a reason other than progressive disease may be followed for efficacy and survival until 1 of the following occurs: the patient progresses, withdraws consent for follow up, or initiates other anti-cancer therapy, or the overall trial is closed.

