7.11 Efficacy and/or Pharmacokinetic and Pharmacodynamic Assessments

7.11.1 Efficacy Assessments

7.11.1.1 Treatment of Patients According to Principles of Immune-Related Response Criteria

Tumor assessments will be obtained at screening using CT and/or MRI scans at time intervals as specified in the [Appendix 1](#) (Time and Events Table). The study is divided into 6 Tumor Assessment Cycles; the first is a 6-week cycle called the Initial Tumor Assessment Cycle and Cycles 2 through 6 are 9-week cycles. The tumor assessment takes place at the end of each cycle. Treatment will continue until patients have completed study therapy and required follow-up, experienced disease progression, or have been withdrawn from the study (see [Section 4.4](#) and [Section 5.3](#)). At each on-treatment tumor assessment time point, the objective response status will be determined. In the context of the statistical analysis for this trial, objective response determination and the assessment of best overall response (BOR) will be defined using both conventional RECIST1.1 criteria ([Appendix 5](#)) as well as an adaptation of these criteria, designated as immune-related response criteria (irRC) (i.e., irRECIST as defined in [Appendix 6](#)). Patient management decisions, however, will be made solely based on the immune-related response criteria ([Appendix 6](#)).

For patients who demonstrate acceptable tolerability of treatment with MGA271, and an objective response assessment of irCR, irPR or irSD, or unconfirmed clinically-stable irPD, therapy may be continued (see [Section 4.4](#) and [Section 5.3](#)).

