For patients who are otherwise clinically stable, but have met conventional criteria for PD, therapy may be continued at the discretion of the investigator pending confirmation of progression at the next scheduled tumor assessment. This approach allows for limited treatment of patients beyond the initial radiographic documentation of disease progression, assuming that patients are tolerating therapy adequately, that patients remain otherwise clinically stable despite this initial radiographic evidence of disease progression and that the Investigator feels the patient may still derive benefit from continuation of therapy. Treatment of patients according to irRC (i.e., irRECIST) principles is supported by well-documented evidence that in some patients treated with T cell directed, immune-modulatory agents, their tumors can evolve to an objective response after an initial period characterized by either apparent radiographic growth of target lesions or the development of new target lesions that would otherwise meet the criteria for disease progression using conventional response criteria ([67](#))

For patients in whom progression is confirmed at the next scheduled tumor assessment, the criteria for immune-related PD (irPD) will have been met, and treatment with MGA271, pembrolizumab, or MGA012 should be discontinued. The patient should be removed from study participation after completion of protocol specified follow-up (see [Section 8.3](#) and [Appendix 1](#)). For patients who experience an objective response of immune-related complete response (irCR) or immune-related partial response (irPR), responses will be considered unconfirmed until the response has been documented by a subsequent confirmatory scan obtained no less than 4 weeks after the initial scan demonstrating an objective response.

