9.5 Efficacy Endpoints

Response will be categorized as CR, PR, SD, or PD and evaluated using RECIST 1.1 criteria ([Appendix 5](#)) and as irCR, irPR, irSD, or irPD using the immune-related response criteria (i.e., irRECIST as defined in [Appendix 6](#)). The ORR will be the proportion of patients in the response evaluable population achieving CR or PR when such responses are confirmed at least 28 days after the initial observation of an objective response. A two-sided 95% exact binomial confidence interval will be calculated around the ORR for each expansion cohort.

Response duration will be calculated for responders as the time from initial response (CR or PR) to the time of PD or death, whichever occurs first. Kaplan-Meier methods will be used to estimate response duration over time and the median response duration. Responders who complete the study without documented PD will be censored at the date of their last tumor assessment.

PFS and irPFS will be calculated as the time from the initial infusion of pembrolizumab or MGA271 until documented disease progression, or death from any cause. Patients with no PFS event (disease progression or death from any cause) will be censored at the date of their last tumor assessment. In addition, PFS and irPFS rates will be calculated at 3-month and 6-

month time points from the first dose of study drug. Kaplan-Meier methods will be used to estimate PFS over time and the median duration of PFS. The method of Brookmeyer and Crowley (9) will be used to construct 95% CIs around PFS estimates of the median and other quartiles for each expansion cohort.

Incomplete and missing data can complicate interpretation of PFS. [Appendix 3](#) describes the handling of these data for the PFS analysis.

Overall survival is defined as the time from the initial infusion of pembrolizumab or MGA271 to death from any cause. Kaplan-Meier methods will be used to estimate the overall survival function. Patients who do not die will be censored at the date that the patient was last known to be alive. In addition, OS will be calculated at 6 months from the first dose of study drug.

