Beginning with Amendment 5, in Cohort 4, 15 mg/kg MGA271 will be administered as an IV infusion over 120 minutes Q3W in combination with 375 mg MGA012 administered as an IV infusion over 60 to 75 minutes Q3W. On dosing days, MGA012 will be administered first, followed by MGA271. The study treatment schema is presented in **Figure 2**.

Figure 2 MGA271 + MGA012 Treatment Schema: Cohort 4

a Patients may receive up to 5 subsequent 9-week treatment cycles of MGA271 + MGA012 depending on response to study treatments

▲ All patients will enter an Efficacy Follow-up Period after receipt of the last dose of study treatment to be followed for up to 24 weeks for survival.

Patients who remain clinically stable and do not experience unacceptable toxicity that necessitates permanent discontinuation of the study drugs, at the completion of the Initial (6-week) Tumor Assessment Cycle, will be eligible to receive additional treatment with MGA271+MGA012. Assuming that the patient remains clinically stable, maintains a response status of SD or better, and does not experience unacceptable toxicity that necessitates permanent discontinuation of the study drugs, patients may receive up to 5 additional 9-week treatment cycles during Subsequent Tumor Assessment Cycles, for a maximum total of 17 doses of MGA271 and 17 doses of MGA012.

All tumor assessments performed following the Initial Tumor Assessment Cycle will occur on Study Day 63 of each Subsequent Tumor Assessment Cycle thereafter. Following the last dose of study drug, all patients will be followed for survival during a 6-month (24-week)

Efficacy Follow-up Period. Patients who discontinue study treatment for a reason other than progressive disease may be followed for efficacy and survival beyond the 6-month (24-week) period until 1 of the following occurs: the patient progresses, withdraws consent for follow up, or initiates other anti-cancer therapy, or the overall trial is closed.

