3.1.4 Efficacy Follow-up Period

The Efficacy Follow-up Period consists of the 6-month (24-week) period following the final dose of study drug (pembrolizumab or MGA271 or MGA012, whichever is last) where patients will be followed for survival via telephone or other electronic contact at 12-week intervals from the start of the period. Patients who discontinue study treatment for a reason other than progressive disease may be followed for efficacy and survival until 1 of the following occurs: the patient progresses, withdraws consent for follow up, or initiates other anti-cancer therapy, or the overall trial is closed.

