6.6.3 Time-to-Event Analyses

Kaplan-Meier methods will be used to estimate cumulative probabilities and quartiles (25th percentile, median, and 75th percentile) of time-to-event endpoints (DoR, PFS, irPFS, and OS). The method of Brookmeyer and Crowley (1) will be used to construct two-sided 95% CIs around the quartile estimates. These calculations will be performed for all patients in cohort expansion by tumor type. Additional analysis may be carried out, by tumor type, on patients in the dose escalation cohort combined with those in the expansion cohort.

DoR will be calculated from the time of initial response (CR or PR) documentation (in patients who have a subsequent confirmation of objective response) to the time of progressive disease or death, whichever occurs first. Patients with CR or PR at time of last assessment will be censored at the time of their last tumor assessment. DoR will be calculated as follows:

DoR (months) = (progression date or death date or date of last tumor assessment – date of initial response+1) / (365.25/12)

PFS is defined as the time from first dose of study drug until documented disease progression or death from any cause, or date of last tumor assessment. A patient will be censored at the time of last assessment if the patient remains progression free at that time. Progression will be assessed using both RECIST 1.1 and irRC. PFS will be calculated as follows:

PFS (months) = (date of progression or date of death or date of last tumor assessment – date of first dose+1) / (365.25/12)

Overall survival (OS) is calculated from the time of first dose until death from any cause. Patients alive at study completion will be censored for analysis purposes. OS will be calculated as follows:

$$\text{OS (months)} = (\text{date of last contact or death date} - \text{date of first dose} + 1) / (365.25/12)$$

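### Does ending survival contact 24 weeks after the last dose spoil the planned overall survival quartiles in the expansion cohorts?

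*Protocol*

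**What the plan says.** Every patient gets 24 weeks of survival follow-up from the last dose of any study drug, during which "patients will be followed for survival via telephone or other electronic contact at 12-week intervals from the start of the period" (Protocol 4.1.4). Protocol 4.1.1 adds: "Patients who discontinue study treatment for a reason other than progressive disease may be followed for efficacy and survival beyond the 6-month (24-week) period". SAP 3.1.1 repeats this. The extension lasts until one of these events: "the patient progresses, withdraws consent for follow up, or initiates other anti-cancer therapy, or the overall trial is closed" (SAP 3.1.4). For confirmed progression, Protocol 7.11.1.1 says: "The patient should be removed from study participation after completion of protocol specified follow-up".

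On analysis, Protocol 9.5 states: "Patients who do not die will be censored at the date that the patient was last known to be alive". SAP 6.6.3 plans the 25th, 50th and 75th OS percentiles with Brookmeyer-Crowley intervals: "These calculations will be performed for all patients in cohort expansion by tumor type". Protocol 9.5 and SAP 5.1 also plan OS at 6 months from first dose.

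Two further points bear on the matter. Protocol 7.11.1.4 leaves the details of OS monitoring to a Study Manual, which is not among the documents. Protocol 9.1 calls the study primarily observational and most summaries descriptive, and the objectives in Protocol Section 3 do not name OS.

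**The concern.** Kaplan-Meier estimation assumes that a patient who leaves follow-up has the same outlook as those who stay. Here a patient who stops for progression has no stated contact after 24 weeks, while a patient without progression stays on treatment, or may be followed longer, and so remains at risk. Progression predicts death. The late part of the OS curve would then rest on the better-prognosis patients, and its upper quantiles would drift upward or never be reached. The SAP plans those quantiles without a caveat or a sensitivity analysis.

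The sponsor already sets response rates from two expansion cohorts beside historical single-agent results (Protocol 2.3.1.1.2, Table 1). An OS quartile that looks long only because telephone contact stopped could be read in the same favorable way.

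**Working it through.** **1. The plan's own schedule.** One 6-week and five 9-week cycles give 6 + 5×9 = 51 MGA271 doses and 2 + 5×3 = 17 pembrolizumab doses, as stated in Protocol 4.1.1. The expansion total is 16 + 16 + 4×20 = 112, as in Protocol 4.7.1. The documents give no OS event target or OS follow-up target.

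**2. When contact ends.** Inputs: 24 weeks = 168 days; weekly dosing to Day 36 of Cycle 1 and Day 57 of later cycles (Protocol Appendix 1, Table 8); Cycle 2 Day 1 = Study Day 43. With the SAP convention, months = (last-dose day − 1 + 168 + 1)/(365.25/12):

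- stop at the Day 42 scan, last dose Day 36: 204/30.4375 = 6.70
- stop at the confirming scan, last dose Day 99: 267/30.4375 = 8.77
- six full cycles, last dose Day 351: 519/30.4375 = 17.05

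**3. Bias from the link with progression.** Illness-death simulation, 400,000 patients per scenario. Assumptions: exponential time to first event with median 2.0 or 2.9 months; 0% or 15% of first events are deaths; exponential post-progression survival solved to give the stated true median OS; scans at Day 42 and every 63 days to Day 357; last dose six days before the stopping scan; OS censored 168 days later. The optional longer follow-up and extra cycles are left out. Shifts are in months against complete follow-up:

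| True median OS | Median: stop at first PD / confirming scan | 75th percentile: stop at first PD / confirming scan |
|---|---|---|
| 8 | +0.04 to +0.10 / 0.00 | +0.56 to +1.04 / +0.19 to +0.35 |
| 10 | +0.07 to +0.40 / 0.00 to +0.07 | not reached |
| 12 | +0.05 to +0.80 / +0.01 to +0.23 | not reached |

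Repeat runs widen the 8-month range for the 75th percentile to about +0.1 to +1.1. The confirming-scan column deserves weight, because "Patient management decisions, however, will be made solely based on the immune-related response criteria" (Protocol 7.11.1.1), and clinically stable patients may be treated until progression is confirmed.

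**4. Is not reached a bias or just short follow-up?** Keep the same model and the same censoring times, but shuffle those times across patients so that they no longer depend on progression. Share of n=20 cohorts with the 75th percentile not reached:

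| True median OS | Linked | Shuffled |
|---|---|---|
| 8 | 18-51% | 25-58% |
| 10 | 53-70% | 52-71% |
| 12 | 74-81% | 69-81% |

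Removing the link does not make the problem go away. At a median of 10 months the true 75th percentile is about 16.6-17.9 months, around the 17.05-month limit from step 2, so many cohorts cannot reach it however censoring arises.

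**5. The planned 6-month rate.** Only very early stoppers leave before 6 months: a last dose on Day 1 gives 169/30.4375 = 5.55 months and on Day 8 gives 176/30.4375 = 5.78. With 5-20% such patients, even with their post-progression survival halved, the largest shift is 0.6756 to 0.6783, or 0.0027. The 25th percentile does not move.

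**6. Scale.** Take the melanoma reference in Protocol 2.1 (median OS about 10 months, median PFS 2.9 months, from another treatment). With complete follow-up, 95% of n=16 cohort medians lie between 5.7 and 15.0 months, a half-width of (15.0 − 5.7)/2 = 4.65. The largest bias in the median at 10 months, 0.40, is 0.40/4.65 = 9% of that. A 75th percentile in cohorts of 16 or 20 has only 4 or 5 patients above it.

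**The case for a change.** The strongest contrary case is that a pre-specified number should be right even when it is descriptive. At n=20 the chance that the 75th percentile is overstated or not reached is 44-75% at a median of 8 months and 53-87% at 10, against 38% with complete follow-up. If 30% of patients have a good prognosis, the large-sample 75th percentile at a median of 8 months can be overstated by up to 78%, or not reached. Better data would help: on the melanoma reference with stopping at first progression, recovering vital status for 80% of censored patients brings the median from 10.43 to 10.08 (true 10.03) and the 75th percentile from not reached to 16.5 (true 16.4). A caveat in the SAP would cost a sentence.

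Much of this stands as description. Late OS quantiles will often be immature, and where they are reached they may be somewhat high. It does not amount to a case for change. At 8 months the lower bound of 44% is close to 38%; the effect is firm only from about 10 months, where not reached dominates and is a truthful Kaplan-Meier result. The references also limit its reach: 178 days (178/30.4375 = 5.85 months) for head and neck cancer falls below the range, and urothelial cancer has no usable median.

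A vital-status sweep means going back to up to 30-40 sites (Protocol synopsis) about cohorts that are closed with treatment complete (Protocol 2.3.1.1.2), possibly with new consent and ethics approval (Protocol 11.1), to sharpen an upper quartile that decides nothing. Continuing the 12-weekly contact would mainly reach Cohort 4, for which SAP 6.6.3 does not specify OS quartiles.

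**Conclusion.** No change to the plan is needed. The link between censoring and progression exists, but its own contribution at a true median of 8 months is about 0.1 to 1.1 months in the 75th percentile and at most 0.1 month in the median. The frequent failure to reach the 75th percentile at medians of about 10 months or more is chiefly the price of short follow-up, a fair trade-off in a Phase 1 study that rests no decision on OS. The OS figure that this follow-up supports well, the 6-month rate, is already planned and moves by less than 0.003.

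The rest is ordinary reporting. Numbers at risk, follow-up time and a remark that late quantiles are immature can accompany the curves without an SAP amendment; table and figure conventions sit in the separate programming plan (SAP Section 7), which cannot be judged here.

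This rests on exponential hazards, a median time to first event of 2.0 or 2.9 months, historical reference figures for other treatments, and no follow-up beyond the protocol text. A marked good-prognosis subgroup would enlarge the bias in the upper quartile; post-progression contact under the Study Manual would reduce or remove it.
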